7.6.3 Statistical analysis of secondary endpoints

Based on the EAS dataset, descriptive analysis will be used to summarize the baseline characteristics of enrolled subjects, changes in nutritional status, metabolic state, residual renal function, and trends in dialysis adequacy at 3 months and 6 months post-treatment, with graphical presentations. For the comparison of changes from baseline: continuous variables will be compared using paired t-tests or Wilcoxon-signed rank tests based on data distribution; for categorical variables, McNemar-tests will be used compare yourself before and after.

7.6.4 safety analysis

Based on the SS set, all AE will be summarized by descriptive analysis. In addition, they will be summarized separately by drug correlation, drug-related treatment measures, outcomes and severity. If necessary, they will be summarized by subgroup (e.g

Data were stratified according to whether dialysis was adequate or heart failure).

Summarize the changes of vital signs, laboratory tests and ECG results of each group relative to baseline, the results with clinical significance after baseline and all test results were listed.

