statistical analysis	
analytic set
 
Full analysis set (Full Analysis Set, FAS): All with at least one exposure subjects studied for treatment. This analysis set will be used primarily for the analysis of baseline data. Set of Safety Analyses (Safety Analysis Set, SS): At least one study was accepted all subjects treated and with a record of safety after medication. Effectiveness Analysis Set (Effectiveness Analysis Set, EAS): All subjects included received at least one study treatment and had at least one post-treatment observation subjects for the evaluation of the effectiveness of the intermediate point.
 
statistical analysis technique
 
Continuous variables will be statistically described according to the data distribution, including number of cases (non-missing), mean, standard deviation, median and quartiles, maximum and minimum values.
 
Calculate the number and percentage of each category of categorical variables.
 
Main endpoint: Descriptive analysis was used to summarize baseline, post-treatment 6 months albumin and prealbumin measurements, and the difference in change from baseline of enrolled subjects. Paired t-tests were used to test for differences before and after treatment, and multiple problems were controlled by Hochberg method.
 
Secondary endpoints: Descriptive analysis will be used to summarize the baseline, three months post-treatment, and six months post-treatment nutritional status, metabolic status, residual renal function, and trends in dialysis adequacy for enrolled subjects, with graphical presentations;
 
Tests for changes relative to baseline: For continuous variables, paired t-tests or Wilcoxon's signed-rank test will be used to compare pre-and post-treatment differences based on data distribution; for categorical

----------------------	---

	
variables, McNemar-tests will be used to compare the behavior before and after.
 
Safety analysis: Descriptive statistics were used to summarize adverse events and adverse reactions, drug-related treatment measures, outcomes, and severity classification. Subgroups were used if necessary(For example, whether dialysis is adequate or heart failure) stratified analysis of data was performed.
 
Exploratory analysis: patients were divided into adequate and inadequate groups according to baseline $Kt/V \geq 1.7$. The improvement of nutritional indicators in different subgroups was analyzed.

--	--

catalogue

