Kt/V: The change value of Kt/V compared with the baseline at 3 months and 6 months ($\Delta Kt/V$), calculated by the formula $Kt/V = (V \times \ln(C0/C1) + (V \times UF)/C1)/V$, where V is the body volume, C0 is the urea nitrogen concentration before infusion, C1 is the urea nitrogen concentration after outflow, and UF is the ultrafiltration measure;

Ccr (L/week): the change value of Ccr compared with baseline at 3 months and 6 months (ΔCcr), calculated by the formula $Ccr = (U \times V)/P$, where U is the concentration of urinary creatinine and V is the urine volume, P is serum creatinine concentration;

- PET: PET change values (ΔPET) at 3 months and 6 months compared to baseline

The formula $PET = (D/P) \times 100\%$ was used to calculate the concentration of substances in the effluent D and P. The concentration of a substance in a filling liquid.

6) Capacity load index

Nt-pro BNP: Nt-pro BNP change values at 3 months and 6 months compared to baseline (Δ Nt-pro BNP); the level of Nt-pro BNP in subjects was measured by electrochemiluminescence.

7) Safety endpoint (adverse event): assessed according to vital signs, physical examination, laboratory tests, etc.

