(1) Informed Consent: Before participants join this study, their written consent, either from the participant themselves or their legal representative, must be obtained. The informed consent form should include information on the purpose, design, process, risks, benefits, rights, and obligations of the study, as well as the participant's personal information and contact details. The informed consent form should be signed jointly by the researcher and the participant or their legal representative. It's kept in the research files.

(2) Collect demographic data: After the subject is selected for this study, basic information should be recorded, including name, gender,

Age, height, weight, BMI, etc. The formula for calculating BMI is: $BMI = \frac{\text{weight (kg)}}{\text{height m}^2}$.

(3) Collect symptoms (loss of appetite, nausea, vomiting, abdominal distension, infusion pain, edema, etc.): After the subject is enrolled in this study, detailed questions should be asked about gastrointestinal related symptoms and edema, which should be recorded in CRF, and attention should be paid to whether there are causes related to this study or influencing factors.

(4) Collecting Past Medical History and Comorbidities: After a participant is enrolled in this study, their past medical history and comorbidities should be thoroughly inquired about. This includes all relevant internal and external medical conditions and surgical histories, as well as any medications currently being used or planned for use, and other treatments. The past medical history and comorbidities should be documented in the CRF, with attention to any factors relevant to this study

Or influencing factors.

(5) Inquiry of allergy history: After the subject is selected for this study, his/her allergy history should be inquired in detail, including allergen, allergic reaction and so on treatment methods, etc. Allergy history should be recorded in the CRF, and pay attention to whether there are factors or influencing factors related to this study.

(6) The improved SGA evaluation method was used. The higher the score, the worse the nutrition. Normal nutrition: 7 points; mild to moderate nutrition: 8-15 points; severe malnutrition: ≥ 16 points.

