(16) Conduct PET testing: After subjects are enrolled in this study, regular PET tests should be conducted to evaluate their peritoneal dialysis material transport characteristics. The PET testing method follows the standard PET (Standard PET) proposed by Twardowski. Measure the glucose concentration in the effluent and compare it with that in the infused fluid to calculate the D/P ratio and the D/D0 ratio. Based on the D/P ratio and the D/D0 ratio, subjects are categorized into four types: high transport, high average transport, low average transport, and low transport. The results of the PET testing should be

recorded in the CRF, noting any abnormalities or differences common associated clinical manifestations.

(17) Adverse events: The recording time is from the start of treatment to the end of survival follow-up, and only AE related to this study is collected, Including adverse events of special concern.

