4.2 Data collection

4.2.1 Screening period

During the screening period, the following observations were performed on patients who met the inclusion criteria:

Informed consent: Explain the purpose, method, benefits and risks of this study to the patient, and obtain his/her written informed consent.

Inclusion/exclusion criteria: Check whether the patient meets the inclusion and exclusion criteria.

Past history/comorbidities/treatment: Record the patient's past history, comorbidities and treatment.

Comprehensive Subjective Nutritional Assessment (SGA): Using the improved method of SGA assessment in the 2010 version of The Standard Operating Procedures for Peritoneal Dialysis, patients were comprehensively assessed for nutritional status, including weight change, appetite change, gastrointestinal symptoms, activity ability and complications, physical examination, etc., and patients were divided according to the scoring results. There are three categories: normal nutrition (A), mild malnutrition (B) or severe malnutrition (C).Physical examination: Measure the patient's height, weight, blood pressure, heart rate, respiratory rate and other indicators, and calculate

BMI (BMI= body mass / height² (kg/m²)).

Blood pressure measurement: Use standardized methods and equipment to measure the patient's systolic and diastolic blood pressure and record itaverage value.

Body weight measurement: Use an electronic scale to measure the dry weight of the patient and record the value.

BMI Calculation: Calculate the patient's BMI based on weight and height data, and record its value.

CI calculation: Use the tape measure to measure the patient's waist circumference, and calculate the patient's CI value ($CI = \text{waist circumference (m)} / \{0.109 \times [\text{body weight (kg)} / \text{height (m)}]^{1/2}\}$) according to the weight and height data, and record it numeric value.

Waist circumference and grip strength measurement: Use a tape measure to measure the patient's waist circumference and record its value. Use a grip strength gauge, according to the standard method, the grip strength of each patient's left and right hands was measured once and the average value was recorded.

Triceps skinfold thickness measurement: Use a skinfold thickness gauge and follow a standardized method on the right side of the patient the triceps, the thickness of the skin fold was measured and recorded.

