4.2.2 During treatment

During the treatment period, each participant received a regimen of 1 bag of amino acid peritoneal dialysis and 2-4 bags of glucose peritoneal dialysis fluid daily for 6 months (the amount of glucose peritoneal dialysis fluid was determined based on the treatment plan at the time of screening when the patient entered the study). In the third and sixth months of the treatment period, participants should repeat all assessments from the screening phase and record any adverse events or serious adverse events. Monthly follow-up evaluations were conducted during the treatment period. Observe (infusion pain, abdominal distension), blood pressure, weight, urine volume, ultrafiltration.

5. Treatment plan

The treatment protocol of this study is as follows:

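### McNemar's test is named for all categorical before-after comparisons, but the SGA class (three ordered levels) and PET transport type (four) are not binary

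*Combined protocol and SAP*

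**What the plan says.** Section 7.6.3 gives two rules for change from baseline. Numeric variables: "continuous variables will be compared using paired t-tests or Wilcoxon-signed rank tests based on data distribution". Everything else: "for categorical variables, McNemar-tests will be used compare yourself before and after". The synopsis repeats the second rule: "McNemar-tests will be used to compare the behavior before and after". Neither place names the categorical variables to be tested, an extension to more than two levels, or a cut that would make a variable binary.

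The protocol defines two graded classifications:

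- **PET transport type.** Section 4.1, item (16): "subjects are categorized into four types: high transport, high average transport, low average transport, and low transport".
- **SGA.** Section 4.1, item (6), bands the score: "Normal nutrition: 7 points; mild to moderate nutrition: 8-15 points; severe malnutrition: ≥ 16 points". Section 4.2.1 likewise sorts patients into three grades, A, B and C.

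Both are measured again on treatment. Section 4.2.2 says that in months 3 and 6 "participants should repeat all assessments from the screening phase", and Table 1 also shows the SGA every month. In the endpoint list of 3.2.2, PET appears only as a numeric change ("PET: PET change values (ΔPET) at 3 months and 6 months compared to baseline"), and the SGA does not appear.

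**The concern.** McNemar's test compares the two discordant cells of a paired 2x2 table. A three- or four-level class has no such table, so an analyst who follows 7.6.3 literally must do something that the plan does not describe. One route is to collapse the classes, and the result then depends on the cut. The other is the symmetry extension (Bowker's test), which asks whether the before-by-after table is symmetric in any way at all. It takes no account of the order of the classes, so it is a blunt tool for the natural question of whether patients moved towards better or worse.

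At stake is how reliably a one-directional shift in nutrition class or transport type would be detected, and whether the analysis of those classes is fixed in advance.

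**Working it through.** **1. The plan's own figures.** Section 7.1 uses one-sided alpha 0.0125 and power 0.90. (2.2414 + 1.2816)² = 12.411.

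- Albumin: 12.411 × 4.5²/1.5² = 12.411 × 9 = 111.7, so 112.
- Prealbumin: 12.411 × (80/60)² = 22.06, so 23.
- With 20% dropout: 112/0.8 = 140.

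All three reproduce, using the squared sum of z values; the printed formula lacks the square. The documents give no power for any categorical comparison. I take 112 as the evaluable number.

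**2. Matching the test to the variables.**

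- SGA class: three ordered levels, repeated. McNemar does not apply. All three levels can occur at baseline, because 3.3.1 requires only two of its three malnutrition criteria and so admits a patient with a normal SGA score.
- PET transport type: four ordered levels, repeated. McNemar does not apply.
- Kt/V at 1.7 and Nt-pro BNP at 11000 pg/mL: two levels, but used as grouping factors (2.3, 4.2.1, 7.6.5), not as before-after outcomes.
- Symptoms at each visit (Table 1): McNemar fits if they are recorded as present or absent.

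**3. What the extension tests.** Bowker's statistic is the sum over class pairs i<j of (n_ij − n_ji)²/(n_ij + n_ji), on k(k−1)/2 degrees of freedom: 3 for three classes, 6 for four. Pairs with no patients contribute nothing, and some analyses drop them from the degrees of freedom. At equal noncentrality, 80% power on 1 df becomes 65% on 3 df and 52% on 6 df.

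**4. Power by simulation.** Every input except n = 112 is an assumption, because the documents give none: a bivariate normal latent variable, a shift of 0.25 SD in one direction, correlation 0.7 or 0.8, class splits of 15/35/35/15% and 10/70/20%, two-sided 5%. The signed-rank test is applied to the change in class number, with a tie correction.

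| Classes | Correlation | Symmetry, full df | Symmetry, non-empty pairs | Signed-rank |
|---|---|---|---|---|
| 4 | 0.7 | 40% | 50% | 82% |
| 4 | 0.8 | 51% | 68% | 91% |
| 3 | 0.7 | 32% | 46% | 60% |
| 3 | 0.8 | 41% | 56% | 71% |

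Repeat runs agreed to within about 4 points. With no change, the full-df test rejects in only about 1-2% of trials, so it is conservative. On non-empty pairs the loss is 82 − 50 = 32 and 91 − 68 = 23 points with four classes, and 60 − 46 = 14 and 71 − 56 = 15 points with three.

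**5. Other assumptions.** Here five other class splits were used, with correlation 0.5 or 0.8, n = 112 or 140, and the shift set so that an ordered 1-df paired test had 80-84% power. The symmetry test on non-empty pairs lost 10-18 points with three classes and 25-32 with four. On full df it lost 18-27 and 37-50. The Stuart-Maxwell test of marginal homogeneity lost 9-12 and 16-18.

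**6. Collapsing.** In the setting of step 4 at correlation 0.7, exact McNemar has 25%, 48% or 31% power with four classes, depending on the cut, and 14% or 37% with three. Every cut is weaker than the ordered test.

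**7. The numeric route.** If the uncut variable is tested, the standardised paired shift is 0.25/√(2 × (1 − 0.7)) = 0.323. Then 0.323 × √112 = 3.42, and 3.42 − 1.96 = 1.46, which gives about 93% power. At correlation 0.8: 0.25/√0.4 = 0.395, then 4.18 − 1.96 = 2.22, about 99%. Simulated paired t-tests gave 92% and 98%.

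**The case against.** The strongest reply is that the two classes are not endpoints. Section 7.6.3 covers secondary endpoints, and the efficacy items in 3.2.2 are numeric changes. Transport type and SGA grade are described as assessments, and nowhere does the plan commit to testing change in them. The same sentence of 7.6.3 already gives numeric variables a t-test or signed-rank test, which covers the D/P ratio and the SGA points, and step 7 shows that this route is the more powerful one. All of this stands, and it limits the consequence.

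It does not remove the gap. Section 7.6.3 promises tests for categorical variables without naming any, and the only graded repeated classifications that the protocol defines do not fit the test it names.

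A reader might infer three stronger things that the documents do not support:

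- **That McNemar is wrong throughout.** It remains valid for yes/no variables such as presence of a symptom.
- **That a safety signal in transport type would be missed.** Section 7.6.4 plans descriptive safety summaries, so the power of a test does not decide what is seen there.
- **That classes will be collapsed after the data are seen, or that Bowker's test will be run.** The plan says neither. These are the options its silence leaves open.

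**Conclusion.** The point holds in limited form, as a minor one. McNemar's test does not apply to the three-level SGA class or the four-level PET transport type, and the plan names no alternative for them. The likely extension is weaker than an ordered test against a one-directional shift: by about 23-32 points with four classes and 14-15 with three in the main setting, on non-empty pairs, and by more on full degrees of freedom. It would be too strong to say that much of the power is lost in every case. With three classes the loss was as low as 9 points for one extension.

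These sizes rest on assumed class splits, correlations and shift, and on change in one direction; a change without consistent direction could favour the symmetry test. The primary endpoints, the sample size and the success criterion are untouched, and 7.7 leaves the other tests outside the multiplicity control.

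**What to change.** In 7.6.3 and the synopsis:

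- Name the categorical variables whose change will be tested.
- For SGA class and PET transport type, use the Wilcoxon signed-rank test on the ordered class, stating how ties and unchanged patients are handled. Apply the same test to the SGA score.
- Show the full before-by-after shift table for each class at months 3 and 6.
- Keep McNemar's test for binary variables, such as presence of a symptom.

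If only the numeric D/P ratio and SGA points are to be tested, say so and present the classes descriptively.

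The cost is a sentence or two in the plan. No new data, visits or patients are needed.

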7.6.5 Exploratory analysis

Patients were divided into adequate and inadequate groups according to baseline $Kt/V \geq 1.7$, and the improvement of nutritional indicators in different subgroups was studied

Analysis of variance. If applicable, differences in the improvement of nutritional indicators will be tested based on different groups of baseline.

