2.3 Exploratory purposes

According to $Kt/V \geq 1.7$, patients were divided into dialysis adequate and non-dialysis adequate groups, and the effects of amino acid peritoneal dialysate on the nutritional status of patients with dialysis adequacy were explored; according to Nt-pro BNP levels, patients

were divided into non-heart failure groups and heart failure groups for further exploration safety of amino acid peritoneal dialysis fluid.

3. Test design

The experimental design of this study is as follows:

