And use a soft ruler. Grip strength measurement should be taken between the thumb and index finger of the right hand, using a standard grip strength gauge. The formula for calculating CI is: $CI = \text{waist circumference (m)} / \{0.109 \times [\text{body weight (kg)} / \text{height (m)}^{1/2}]\}$. Waist circumference, grip strength, upper arm muscle

The results of the peritoneal and CI should be recorded in the CRF, noting any abnormalities or abnormal related clinical manifestations.

(12) Biochemical blood tests: After the subjects are enrolled in this study, regular biochemical blood tests should be performed, including ALT (alanine transaminase), AST (aspartate transaminase), total bilirubin, direct bilirubin, blood urea nitrogen or urea, total protein, albumin, creatinine, blood glucose, lactate dehydrogenase, K^+ , Na^+ , Ca^{2+} , Cl^- , etc., to evaluate their liver function, kidney function and metabolism

Level. The results of biochemical blood tests should be recorded in the CRF and note any abnormalities or abnormal related clinical manifestations.

(13) Detection of Nt-pro BNP: After the subjects were enrolled in this study, screening period and treatment at 3 months and 6 months Nt-The results of the pro BNP should be recorded in the CRF, noting any abnormalities or abnormal related clinical manifestations.

(14) Detection of nPCR and nPNA: After the subject is enrolled in this study, his/her nPCR and nPNA should be regularly tested to evaluate his/her protein catabolism rate and total protein nitrogen presentation rate. The results of nPCR and nPNA should be recorded in the CRF and noted whether there are any abnormal or abnormal related clinical manifestations.

(15) Calculate Kt/V and Ccr: After the subject is enrolled in this study, Kt/V and Ccr should be calculated regularly to evaluate his/her dialysis efficiency and residual renal function. The results of Kt/V and Ccr should be recorded in the CRF, and attention should be paid to any abnormalities or abnormal related conditions clinical manifestations.

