7.1 Sample size calculation

This study is a post-marketing study, and a total of 140 subjects are planned to be included. The efficacy evaluation standard is 6 months of treatment

If the difference between the post-relative baseline change of Δ serum albumin or Δ prealbumin is statistically significant, it is considered

The treatment was effective. Based on the above hypothesis, a single sample self-preceding and following control design and a unilateral difference test were used

Quantity estimation formula:

$$n = \frac{(z_{\alpha} + z_{\beta}) \sigma^2}{\delta^2}$$

δ is the difference; σ is the standard deviation, which will be replaced by the sample size standard deviation.

The Hochberg method was considered to adjust for multiple endpoints, with the smallest test level $\alpha/2= 0.0125$ (one-sided) and power $(1- \beta) = 0.9$, based on the sample size estimates for different primary efficacy endpoints count.

1) Based on Δ serum albumin: According to the literature, it is assumed that the baseline serum albumin before treatment is 27 g/L, and the serum albumin after 6 months of amino acid peritoneal dialysis treatment is 28.5g/L, δ is 1.5g/L, and the standard deviation is 4.5 g/L,

The required sample size for the calculation was 112.

2) Based on Δ prealbumin: According to the literature, it is assumed that the baseline prealbumin before treatment is 240 mg/L, the prealbumin 6 months after amino acid peritoneal dialysis treatment is 300mg/L, δ is 60mg/L, and the standard deviation is 80 mg/L, the required sample size for calculation is 23 cases.

In order to ensure that the final analysis of this study has enough sample size, considering the possible loss to follow-up, withdrawal, invalid data and other situations, the maximum sample size of 112 cases estimated based on the above two indicators will be increased by 20%

The dropout rate was expanded to a total sample of 140 cases.

7.2 analysis set

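### The only planned look at whether nutritional gain depends on dialysis adequacy splits baseline Kt/V at 1.7; a regression on Kt/V as measured should be added beside it.

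*Combined protocol and SAP*

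**What the plan says.** Section 7.6.5 (Exploratory analysis) defines the comparison: "Patients were divided into adequate and inadequate groups according to baseline" Kt/V of at least 1.7. The method follows in a broken, translated sentence: "Analysis of variance. If applicable, differences in the improvement of nutritional indicators will be tested based on different groups of baseline". The statistical-analysis row of the summary repeats the split and says that improvement in the subgroups was analysed, without naming a test.

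Section 2.3 (Exploratory purposes) frames the objective the same way: "patients were divided into dialysis adequate and non-dialysis adequate groups", with the effect on nutritional status then explored. It is the only efficacy question in 2.3; the other item there, grouping by Nt-pro BNP, concerns safety.

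The underlying value is available for every patient. Section 4.1, item (15), states that "Kt/V and Ccr should be calculated regularly to evaluate his/her dialysis efficiency and residual renal function". Table 1 schedules Kt/V at screening, month 3 and month 6, and section 4.2.1 lists it among the screening calculations. No section plans an analysis of nutritional change against Kt/V as a continuous variable.

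**The concern.** Splitting a measured variable discards the ordering within each group. Under this plan a patient at 1.69 counts as different from one at 1.71 and as the same as one at 1.2. The documents give no reason to expect nutritional response to change abruptly at 1.7. They also do not say what share of patients should fall on each side.

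If the gain in albumin or prealbumin rises or falls gradually with adequacy, a two-group comparison detects this less often than a regression on the same data. At stake is how informative one exploratory question is. The trial's success rule in 3.2.1, 7.1 and 7.7 is not touched.

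**Working it through.** **1. The plan's own figure.** Section 7.1 gives a one-sided level of 0.0125, power 0.90, and for albumin "δ is 1.5g/L, and the standard deviation is 4.5 g/L".

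n = ((z(0.9875) + z(0.90)) × SD / δ)² = ((2.2414 + 1.2816) × 4.5 / 1.5)² = 111.70, so 112. Allowing for 20% dropout, 112 / 0.8 = 140.

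Both stated figures reproduce. (The formula as printed lacks the square on the sum of the z values, but the stated result uses it.) This calculation covers the primary endpoints only. The documents state no power for the Kt/V comparison.

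**2. Inputs for the Kt/V comparison.** From the documents: the cut at 1.7, and 112 evaluable patients as the planning number. Assumed, because the documents do not give them: a two-sided 5% level, approximately normal Kt/V, a linear relation, the correlation r between Kt/V and change, and the share of patients on each side of 1.7.

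**3. Information kept by the split.** With normal Kt/V and a linear relation, a split leaving share p on one side multiplies the non-centrality by k = φ(z_p) / √(p(1−p)). The share of information kept is k².

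| Split | k² | Equivalent patients out of 112 |
|---|---|---|
| 50:50 | 0.637 | 0.637 × 112 = 71 |
| 70:30 | 0.576 | 0.576 × 112 = 65 |
| 80:20 | 0.490 | 0.490 × 112 = 55 |
| 90:10 | 0.342 | 0.342 × 112 = 38 |

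This step needs no assumed correlation.

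**4. Power, analytically.** If the continuous test has 80% power, its non-centrality is 1.960 + 0.842 = 2.802. At 50:50, k = 0.798, and power becomes Φ(2.802 × 0.798 − 1.960) = 61%, a loss of 19 points. At 80:20, k = 0.700, and power becomes 50%, a loss of 30 points. Starting from 90% power, the losses are 17 and 28 points.

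**5. Power, by simulation** (20,000 data sets per setting, n = 112, t-test of the correlation):

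| r | Split | Kt/V as measured | Split at cut | Loss (points) |
|---|---|---|---|---|
| 0.20 | 50:50 | 57.0% | 39.5% | 17.5 |
| 0.20 | 80:20 | 56.5% | 30.9% | 25.6 |
| 0.26 | 50:50 | 79.6% | 60.1% | 19.5 |
| 0.26 | 80:20 | 80.1% | 48.6% | 31.5 |
| 0.30 | 50:50 | 90.0% | 73.2% | 16.8 |
| 0.30 | 80:20 | 90.0% | 60.2% | 29.8 |

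The loss is therefore about 17 to 31 points in this range. Simulation error on each power is at most about 0.35 points.

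**6. Wider inputs.** With the continuous test at 30% to 95% power and splits from 50:50 to 90:10, the analytic loss runs from 9.2 to 42.6 points. Simulations over r = 0.15 to 0.35 and n = 112 or 140 reach slightly further, from 6.3 (n = 140, r = 0.35, 50:50) to 44.7 (n = 140, r = 0.26, 90:10).

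**7. The opposite case.** If the true effect is a step exactly at the cut, the result reverses. At n = 112 and r = 0.25, the split has 77.0% power against 57.3% for the continuous test at 50:50, and 76.4% against 45.5% at 80:20. Over r = 0.25 to 0.30 the split is ahead by about 17 to 31 points.

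**The case against.** The strongest reply is that the objective is about groups. Section 2.3 asks about patients classed as adequately dialysed. The cut is fixed in advance, and the summary, 2.3 and 7.6.5 all use it. A slope answers a related but different question, and under a threshold effect the split is the better test. This stands, and it is why the comparison at 1.7 should be kept. It does not argue against adding the regression, because the documents do not claim a threshold in nutritional response.

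A second reply concerns the inputs. The documents give no correlation, no Kt/V distribution, no share below 1.7 and no significance level for this test. Even 112 is a planning number: the EAS in 7.2 keeps anyone with one valid post-treatment evaluation, and 7.5 fills gaps by LOCF, so up to 140 patients could be analysed. At n = 140, with r = 0.20 to 0.30 and splits from 50:50 to 80:20, the simulated loss is about 13 to 30 points. All of this stands. A reader might infer that the plan as written loses 17 to 31 points of power. The documents do not support that, because the figure is conditional on inputs they do not contain.

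Third, the test itself is less definite than it may seem. The reference to analysis of variance is a fragment in a broken sentence, the summary names no test, and the difference test is only conditional. One cannot say that the plan firmly commits to an ANOVA. However, any two-group test on the split has the same loss under a linear relation.

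Finally, a reader might infer that the trial would go on to report that the effect does not depend on adequacy. No section contains a decision rule for this analysis or treats a non-significant exploratory result as evidence of no dependence. It is a possible misreading to guard against, and the plan does not prescribe it.

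**Conclusion.** The point holds as a minor improvement. Baseline Kt/V is used only as a split at 1.7, and no analysis uses the measured value. Under approximate normality and linearity the split keeps about 64% of the information at 50:50 and about 49% at 80:20. Under the further assumptions of n = 112, two-sided 5% and r = 0.20 to 0.30, this means about 17 to 31 points of power, or about 9 to 43 over wider assumptions. The advantage reverses if the true effect is a step at 1.7.

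Materiality is low. The analysis is labelled exploratory, has no endpoint of its own (3.2.3), has no stated power, and does not enter the primary conclusion. Nothing here questions 1.7 as a clinical adequacy criterion, and the documents do not support dropping the comparison at that value.

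**What to change.** In 7.6.5, keep the pre-specified comparison at 1.7 and add one sentence to this effect:

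> In addition, the month-6 change in serum albumin and in prealbumin will each be regressed linearly on baseline Kt/V as a continuous variable. The slope per 0.1 Kt/V will be reported with its 95% confidence interval, and a scatter plot will be used to check linearity. A non-significant difference between the two adequacy groups will not be interpreted as evidence that the effect does not depend on adequacy.

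The confidence interval has its own value: it shows how large a dependence the data can exclude, which the group comparison conveys less well.

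The cost is one sentence and one regression per marker, on data already collected, with no new visits or measurements. There are two downsides. One is an extra exploratory test per marker, unadjusted, as 7.7 already provides for non-primary tests. The other is the linearity assumption, which the scatter plot addresses. Other nutritional indicators can stay with the group comparison, which limits the number of added tests.
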